2.1.2 Secondary Objectives

The secondary objectives of this study are:

- To evaluate the safety and tolerability of ferric maltol and intravenous iron (IVI, FCM) in subjects over a treatment duration of up to 52 weeks.
- To evaluate long-term healthcare resources utilized in the management of IDA in IBD.

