2.3.3 Pharmacoeconomic Endpoints

Pharmacoeconomic measures include the following:

- Number of hospital or clinic visits for administration of IV Iron.
- Proportion of subjects who restart IV iron during the study.
- Quality of life as assessed by the Medical Outcomes Study 36-item short form questionnaire.
- Correction and Maintenance of IDA
 - Repeat Hb or iron testing
 - Method of transportation to attend each visit.
 - The number of days off work or school/education to attend hospital or clinic visits for administration of IV Iron.
 - The time spent in the hospital or clinic receiving IV Iron.
 - The total dose of IV Iron administered over the study period.

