3 STUDY DESIGN

3.1 Overall Study Design

This study will be a Phase 3b, multicentre, open-label, active-controlled, randomized, parallel group prospective study to compare the efficacy and safety of ferric maltol to IV Iron in subjects with inflammatory bowel disease. A total of 242 subjects from 35-45 European sites and around 18 United States sites will be randomized at a ratio of 1:1 to the two treatment arms of this study.

The randomization will be stratified according to screening Hb (<10g/dL or ≥ 10g/dL for Female; < 11g/dL or ≥ 11g/dL for Male) and by IBD subgroup (ulcerative colitis [UC] or Crohn's disease [CD]). Subjects who are re-screened will have their re-screen Hb substituted in lieu of screening Hb for purposes of determining the strata for randomization.

Protocol amendment 7.0 updated the study duration from 52 weeks to 12 weeks. For subjects who entered the study under the previous protocol for the 52 weeks open-label design and completed their study beyond the 12 weeks treatment period, the next scheduled visit will be their End of Study Visit. Otherwise, subjects after the eligibility screening period will enter a 12 weeks treatment period.

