3.2.2 Treatment Period (Visits 2-7)

The Treatment Period begins on the day for which the subject receives their first dose of a study drug (Visit 2/Day 0) and ends on the day corresponding with Visit 7 for those subjects enrolled prior to protocol amendment 7.0, and the day corresponding with Visit 4 for those subjects enrolled under protocol amendment 7.0. Eligible subjects will be randomized in a 1:1 ratio to receive treatment with either oral ferric maltol or intravenous iron.

Subjects randomized to the oral ferric maltol treatment arm will self-administer study medication twice daily; first thing in the morning at least 1 hour before food and concomitant medications, and last thing at night before bed at least 2 hours after food and concomitant medications. Capsules must be taken on an empty stomach with water only. There should be at least an 8-hour gap between doses. These subjects will maintain treatment with oral ferric maltol for the duration of the Treatment Period.

Subjects randomized to the intravenous iron treatment arm will receive IV Iron in accordance with the dosing instructions as per the local summary of product characteristics (SPC)/Prescribing Information (PI). Initial dosing will be as per local SPC/PI, with the number of IV Iron doses administered being calculated based on the subject's starting Hb and weight. For ongoing treatment decisions, ferritin will be measured at Visits 4 (Week 12) and Visits 5 and 6 (Week 24, and Week 36) for patients prior to protocol amendment 7.0. Subjects continuing after Week 12 who are iron deficient (ferritin below 100ng/mL) at any of Visits 4-6 will receive additional IV Iron doses according to the formula in the local SPC/PI.

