10.2 Correction and Maintenance of IDA

Status (yes or no) of administration of IV Iron will be documented at each visit (scheduled or unscheduled) over the Treatment Period for subjects randomized to the IV Iron treatment arm, commencing with the assessment conducted post-randomization at Visit 2. The total number of visits (scheduled and unscheduled) of administration of IV Iron over the Treatment Period will be calculated for each subject randomized to the IV Iron treatment arm. A summary of administration of IV Iron will be provided using descriptive statistics by visit, including a visit labelled "unscheduled", over all visits, and over Post-Day 0 visits. The summaries over all visits and Post-Day 0 visits will capture the respective number of hospital visits for administration of IV Iron and restart of IV Iron pharmacoeconomic endpoints. Missing values of administration of IV Iron will be kept as missing in the summary. A data listing of dose administration will be provided by subject.

Details of IV Iron dosing at the study site include: the duration of time (hours) spent at the study site for IV Iron administration; the dose (mg) of IV Iron

administered at the study site; and, the number of days off work (or, school/education or childcare) that the subject is required to miss due to administration of IV Iron at the study site, will be documented at each visit (scheduled or unscheduled) over the Treatment Period for subjects randomized to the IV Iron treatment arm. A summary of these IV Iron dosing details will be provided using descriptive statistics by visit (including a visit labelled "unscheduled"). A data listing of IV Iron dosing details will be provided by subject.

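### IV iron visit counts and the restart summary pool subjects followed for 12 to 52 weeks, so mean visits fall below the 52-week value and the restart proportion is off in an unknown direction

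*SAP*

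**What the plan says.** One secondary objective in SAP v3.0 section 2.1.2 is "To evaluate long-term healthcare resources utilized in the management of IDA in IBD". The matching endpoints in section 2.3.3 include the number of visits for IV iron administration and "Proportion of subjects who restart IV iron during the study".

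Follow-up differs by design. Under section 3.2.2 the Treatment Period "ends on the day corresponding with Visit 7 for those subjects enrolled prior to protocol amendment 7.0" and on "the day corresponding with Visit 4 for those subjects enrolled under protocol amendment 7.0". Section 3.1 adds that, for earlier subjects already past Week 12, "the next scheduled visit will be their End of Study Visit", which can be Week 24, 36 or 52. Planned re-dosing is tied to continuation: "Subjects continuing after Week 12 who are iron deficient (ferritin below 100ng/mL) at any of Visits 4-6 will receive additional IV Iron doses" (section 3.2.2).

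Section 10.2 takes no account of this. It says "The total number of visits (scheduled and unscheduled) of administration of IV Iron over the Treatment Period will be calculated for each" subject in the IV arm, and then: "A summary of administration of IV Iron will be provided using descriptive statistics by visit, including a visit labelled" unscheduled, over all visits, and over visits after Day 0. The all-visits summary stands for the visit endpoint and the Post-Day 0 summary for restart. Section 10 sets the ITT population, and section 6.7 makes the analysis population the denominator for percentages. No follow-up time, at-risk denominator or split by planned duration is specified.

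The post hoc SAP (section 10) refers back to v3.0 for these analyses. It adds a Kaplan-Meier plot of time to first additional or rescue IV iron on or after Visit 4, without amendment 7 subjects, and total IV iron in 52-week completers.

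**The concern.** A per-subject count is interpretable when every subject is observed for about the same time. Here some subjects are observed for 12 weeks and others for up to 52, and the mix depends on when amendment 7.0 took effect. The pooled mean describes neither a 12-week nor a 52-week course.

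The restart figure has two separate problems. Its denominator includes subjects who stop at Week 12 and so are never at risk of planned re-dosing. Its numerator, any administration after Day 0, cannot tell a restart from completion of the initial course. What is at stake is whether the long-term resource objective yields figures that can be used, for example in an annual cost estimate.

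**Working it through.** The SAP states no figure for IV iron visits or restarts, so there is nothing to reproduce. It also does not give the share of the arm enrolled under amendment 7.0, the re-dose probability or the number of initial visits. Everything below rests on assumed ranges.

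**Mean visits.** Assume 2 initial visits per subject, one visit per re-dose, re-dose probability p at each of Weeks 12, 24 and 36, a share f of the IV arm followed to Week 52, and the rest stopped at Week 12. Stops at Week 24 or 36 and dropout are ignored.

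- 52-week mean = 2 + 3p
- Pooled mean = 2 + 3pf
- Relative shortfall = 3p(1 − f) / (2 + 3p)

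| p | 52-week mean | f = 0.3 | f = 0.5 | f = 0.7 |
|---|---|---|---|---|
| 0.2 | 2.6 | 2.18 (−16%) | 2.30 (−12%) | 2.42 (−7%) |
| 0.4 | 3.2 | 2.36 (−26%) | 2.60 (−19%) | 2.84 (−11%) |
| 0.6 | 3.8 | 2.54 (−33%) | 2.90 (−24%) | 3.26 (−14%) |

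**Restart, denominator alone.** If 40% of subjects who continue past Week 12 are truly re-dosed, the proportion over all IV-arm subjects is 0.4f. That is 36%, 30%, 20% or 10% when 90%, 75%, 50% or 25% continue.

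**Restart, numerator.** The country table in section 10 of the post hoc SAP shows which initial courses need more than one administration:

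- For 1500 mg or 2000 mg with a weekly maximum of 1000 mg, 1500/1000 and 2000/1000 both round up to 2.
- For 1000 mg at 45 kg with a limit of 20 mg/kg, the maximum is 20 × 45 = 900 mg, so 2.
- For 1000 mg at 60 kg, 1 is enough.
- The US course is listed as two doses 7 days apart.

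Each second infusion falls after Day 0 and enters the restart summary.

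**Both effects together.** Let q be the share with a second initial-course infusion after Day 0, independent of re-dosing. The reported proportion with any Post-Day 0 administration is q + (1 − q) × f × 0.4, where f is now the share continuing past Week 12 and the true value is 40%:

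| f | q = 0.25 | q = 0.50 | q = 0.75 |
|---|---|---|---|
| 0.25 | 32.5% | 55% | 77.5% |
| 0.50 | 40% | 60% | 80% |
| 0.75 | 47.5% | 65% | 82.5% |

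The result can lie below, at or above 40%. At q = 1 it is 100% whatever f is.

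**Would one pooled rate solve it?** Mean follow-up is 12(1 − f) + 52f weeks. At f = 0.5 and p = 0.4 that is 32 weeks, or 32/52 = 0.615 years, so the rate is 2.6/0.615 = 4.2 visits per year against a 52-week mean of 3.2 (+32%). Over the grid the overstatement runs from 12% (f = 0.7, p = 0.6: 3.26/(40/52) = 4.24 against 3.8) to 82% (f = 0.3, p = 0.2: 2.18/(24/52) = 4.72 against 2.6). Initial-course visits fall at the start, so a rate pooled across both periods exceeds annual use.

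**The case against.** The strongest reply is that these are descriptive summaries of one arm, with no test and no between-arm comparison, and that much of the information appears elsewhere. Section 10.2 gives by-visit summaries and listings by subject. The post hoc SAP adds a censored time-to-event plot without amendment 7 subjects and a total dose in 52-week completers. Section 2.3.3 also defines restart simply as during the study.

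Most of this stands as a limit on importance, but it does not remove the point. The by-visit percentages still use the analysis population as denominator. The two later displays are post hoc, do not replace the v3.0 visit and restart summaries, and give no visit rate for the period after Week 12.

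Three stronger readings should be resisted:

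- A reader might infer that restart is understated in proportion to the share stopped at Week 12. That would follow only if restart meant true re-dosing. Section 10.2 uses any Post-Day 0 administration, which also counts later initial infusions, so the net bias can be zero or upward.
- A reader might infer that amendment 7.0 subjects could never receive further IV iron. The documents show only that they had no planned re-dosing; section 5.3 foresees IV iron outside the protocolled dose.
- A reader might take total visits over total patient-years as the natural remedy. On the same assumptions it errs upward by 12% to 82%.

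**Conclusion.** The point holds in limited form. Section 10.2 pools visit counts and the restart summary over subjects with 12 to 52 weeks of planned follow-up, including subjects with no protocol re-dosing opportunity. The pooled mean number of visits lies below the 52-week value, by 7% to 33% under the assumed inputs. That direction follows from the design whenever some subjects stop early and some of those who continue are re-dosed; the size cannot be computed from the documents. The restart proportion is misstated in an unknown direction, because the denominator dilutes it and the numerator inflates it. The consequence is confined to descriptive IV-arm summaries serving the long-term resource objective. No efficacy conclusion depends on them, so this is a minor improvement.

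**What to change.** In section 10.2, report IV iron visits in two parts:

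- **Initial course:** visits up to, but not including, any additional dosing at Visit 4, in all IV-arm subjects.
- **Additional IV iron:** visits on or after Visit 4, only in subjects who continued past Visit 4, with their follow-up time. A rate per patient-year may be given for this period only and should not be combined with the initial course.

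Define restart as the first additional IV iron on or after Visit 4, matching the event already used for the Kaplan-Meier plot in the post hoc SAP. Use subjects who continued past Visit 4 as the denominator, and censor at end of study those stopped at Week 24 or 36.

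The cost is SAP wording and one derived variable for follow-up time, with no new data collection. The downside is fewer subjects in the summary after Week 12.

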The method of transportation (Public, Own transport, Hospital provided, Unknown) will be documented at each visit (scheduled or unscheduled) over the Treatment Period. For each scheduled visit, a multinomial logistic regression modelling approach will be used to estimate the visit-specific relative odds of taking a given transportation method to that of Public (i.e., Public transportation will serve as the reference level) between the two treatment arms, adjusted for the effects of baseline Hb (below the observed median or at least the observed median) and IBD subgroup. The "Unknown" method of transportation will be considered as a missing value of method of transportation for purposes of the modelling described here. A summary of Public transportation will be presented using descriptive statistics by visit (including a visit labelled "unscheduled"). The summary will also present, by scheduled visit, the estimated relative odds of taking a given transportation method to that of Public between the two treatment arms, the corresponding 95% CI for the odds ratio, and the p-value from testing the null hypothesis of no association between treatment arm and chosen transportation method.

A data listing of correction and maintenance of IDA will be provided by subject.

11 SAFETY ANALYSES

Unless otherwise noted, the Safety Population will be used for all analyses, summaries, and listings of safety endpoints.

11.1 Adverse Events

An AE is any unfavourable or unintended sign, symptom, or disease temporally associated with the use of an investigational product or protocol-imposed intervention, regardless of attribution. All observed or volunteered AEs regardless of suspected causal relationship to the investigational product(s) will be reported.

All reported terms (investigator descriptions) for AEs will be coded using the most recent version of the Medical Dictionary for Regulatory Activities (MedDRA) and summarised with frequencies and percentages by treatment group, system organ classification, and preferred term.

The number, intensity, relation to study medication and action taken will be described by incidence tables. Subjects with multiple intensities for the same AE will be categorized by the maximum intensity experienced. Subjects with instances of the same AE recorded as both related and unrelated to study medication will be categorized as related. Subjects with multiple actions taken within the same AE will be categorized according to the worst case. Actions taken are discontinued, interrupted, dose reduced, and none (listed from worst case to best case).

The most relevant AE dataset will be the treatment emergent adverse effects (TEAEs), defined as those that occur on or after the day of first dose of study medication and up to 14 days after the last dose of study medication. Multiple instances of the TEAE in each system organ class and multiple occurrences of the same preferred term will be counted only once per subject. When an adverse event occurs more than once for a subject, the maximum severity, causality, and action will be used. The number and percentage of subjects in the following categories will be summarised by group and overall: subjects with AE, TEAE, SAE, Deaths, TESAE, TE Deaths, TEAE related to study treatment, TESAE related to study treatment, and TE deaths related to study treatment.

The following tables will also be presented by treatment arm:

- All TEAEs (including TEAEs by intensity, relation to study medication, and action taken)
- Serious TEAEs
- AEs leading to premature discontinuation of study medication.

Separate data listings will be presented for all AEs, all SAEs, and all deaths.

11.2 Laboratory Evaluations

Clinical laboratory evaluations include the haematology, iron marker, basic

chemistry, liver function, and urine pregnancy test results (for all females of childbearing potential; data will be provided in a data listing).

Laboratory values, change from baseline (haematology and iron markers only) will be summarised using descriptive statistics by category, laboratory test, and visit for each treatment arm and overall.

Laboratory data, including normal ranges and abnormal laboratory flags, will be provided in data listings.

11.3 Vital Signs

Vital signs (blood pressure and heart rate), along with height and weight, will be collected at screening and will be summarised using descriptive statistics. Vital signs, height, and weight will be provided in a data listing by subject.

11.4 Physical Examination

Findings from the screening physical examination will be listed by subject.

12 PRIMARY ANALYSIS

Not applicable

13 FINAL ANALYSIS

The final, complete analysis will be conducted after the last subject completes or discontinues the study and the resulting clinical database has been cleaned, quality checked, and locked. The assignment of subjects to the analysis populations, as described in Section 5, will be the same as in the primary analysis.

The final analysis will then be performed and will include all safety data and efficacy results up-to-and including Follow-up. Results of this analysis will be reported in the CSR.

14 CHANGES FROM PROTOCOL

The Safety population is defined in the protocol as all subjects who have had at least one dose of study drug and one subsequent contact with the Investigator. This has been updated so that the safety population will only consist of subject who received at least one dose of a study drug for consistency with ICH definitions.

A two stage analysis of the safety and efficacy data was detailed in the protocol, with the first stage being conducted when all subjects have completed 12 weeks of treatment, and the second stage being the final analysis. Due to the shortening of the study period, it is anticipated that when all patients have completed 12 weeks

of treatment there will be no patients ongoing in the study, and so only one analysis will be performed.

Other pharmacoeconomic endpoints have been specified here as they are not explicitly mentioned in the protocol. These are:

- Quality of life as assessed by the Medical Outcomes Study 36-item short form questionnaire.
- Correction and Maintenance of IDA
 - Repeat Hb or iron testing
 - Method of transportation to attend each visit.
 - The number of days off work or school/education to attend hospital or clinic visits for administration of IV Iron.
 - The time spent in the hospital or clinic receiving IV Iron.
 - The dose of IV Iron administered.

1 INTRODUCTION

This document describes the statistical methods and data presentations to be used in the revised and post-hoc summary and analysis of efficacy data from Protocol ST10-01-304. The reader is referred to the study protocol and electronic case report forms (eCRFs) for details of study conduct and data collection, and the final statistical analysis plan version 3.0 dated 14 February 2019 for background information and details of the original analysis where applicable.

2 STUDY OBJECTIVES, TREATMENTS, AND ENDPOINTS

For details of the study objectives, treatment group comparisons and non-primary endpoints refer to Statistical Analysis Plan v3.0, dated 14 February 2019.

The primary efficacy endpoint is the proportion of subjects achieving either a $\geq 2\text{g/dL}$ increase in Haemoglobin (Hb) OR normalization of Hb ($\geq 12\text{g/dL}$ for women, $\geq 13\text{g/dL}$ for men based on the WHO definition (WHO/NMH/NHD/MNM/11.1) at Week 12 [*Post-hoc change from previous SAP, noted in the original CSR, from $>12.0\text{ g/dL}$ (women) or 13.0 g/dL (men)*].

Note: the WHO definition of Hb normal limit ($\geq 12\text{g/dL}$ for women, $\geq 13\text{g/dL}$ for men) was applied in the primary efficacy endpoint but not the secondary efficacy endpoints in the original analysis for CSR v1.0.

In this post-hoc analysis, all secondary endpoints that use normal limits will also be based on the WHO definition.

3 STUDY DESIGN

For details of the overall study design and the schedule of study assessments, refer to Statistical Analysis Plan v3.0, dated 14 February 2019.

4 POWER AND SAMPLE SIZE CONSIDERATIONS

Refer to Statistical Analysis Plan v3.0, dated 14 February 2019.

5 ANALYSIS POPULATIONS

For details of the randomized, safety, and ITT populations, refer to Statistical Analysis Plan v3.0, dated 14 February 2019, Section 5.1 to 5.3.

For details of the PP population, refer to Statistical Analysis Plan v3.0, dated 14 February 2019, Section 5.4 and Section 8 below. To clarify, data of the subjects with major protocol deviations occurring after Week 12 were excluded from the PP analysis of the long-term endpoints from that point of deviation onwards in the original analysis for CSR v1.0.

Patients data are re-evaluated with a focus on visit window, drug compliance, missing data, and the allowance of immunosuppressants. A re-evaluated PP population is defined for the post hoc analyses.

Two sensitivity PP population will be determined for the analysis of the primary efficacy data:

The modified PP population for compliance (mPP compliance) contains all patients from the re-evaluated PP population, along with all patients who are only excluded from the re-evaluated PP population due to compliance issues.

The modified PP population for windowing (mPP windowing) contains all patients from the re-evaluated PP population, along with all patients who are only excluded from the re-evaluated PP population due to Week 12 windowing issues for haemoglobin.

Data of the subjects with major protocol deviations occurring after Week 12 are excluded from the re-evaluated PP analysis of the long-term endpoints from that point of deviation onwards.

6 CONSIDERATIONS FOR DATA ANALYSIS

For details of the programming environment, strata and covariates, subgroups, multiple comparisons and multiplicity, significance level, and statistical notation and methodology, refer to Statistical Analysis Plan v3.0, dated 14 February 2019.

Any analysis based on the PP population in the original SAP will be rerun based on the re-evaluated PP population.

Post hoc analyses will be clearly identified as such both in this document and in the Clinical Study Report. Any outputs that are generated post hoc due to re-evaluations of the statistical methods or re-evaluated PP populations will be labelled "Post-Hoc" followed by the month/year run and the table number, Eg "Post Hoc July 2020 Table 14.1.1". Outputs that are updated due to a correction in methods to that described in the Statistical Analysis Plan v3.0, dated 14 February 2019 will be labelled "Revised" followed by the month/year run and the table number, Eg "Revised July 2020 Table 14.1.1".

